#### 11.1.3.1 Evaluation of Target Lesions

**Complete Response (CR):** Disappearance of all target lesions. Any pathological lymph nodes (whether target or non-target) must have reduction in short axis to <10 mm.

Partial Response (PR): At least a 30% decrease in the sum of the diameters of target lesions, taking as reference the baseline sum diameters.

Progressive Disease (PD): At least a 20% increase in the sum of the diameters of target lesions, taking as reference the smallest sum on study (this includes the baseline sum if that is the smallest on study). In addition to the relative increase of 20%, the sum must also demonstrate an absolute increase of at least 5 mm. (Note: the appearance of one or more new lesions is also considered progressions).

Stable Disease (SD): Neither sufficient shrinkage to qualify for PR nor sufficient increase to qualify for PD, taking as reference the smallest sum diameters while on study.

#### 11.1.3.2 Evaluation of Non-Target Lesions

Complete Response (CR): Disappearance of all non-target lesions and normalization of tumor marker level. All lymph nodes must be non-pathological in size (<10 mm short axis).

Note: If tumor markers are initially above the upper normal limit, they must normalize for a patient to be considered in complete clinical response.

Non-CR/Non-PD: Persistence of one or more non-target lesion(s) and/or maintenance of tumor marker level above the normal limits.

Progressive Disease (PD): Appearance of one or more new lesions and/or *unequivocal progression* of existing non-target lesions. *Unequivocal progression* should not normally trump target lesion status. It must be representative of overall disease status change, not a single lesion increase.

Although a clear progression of “non-target” lesions only is exceptional, the opinion of the treating physician should prevail in such circumstances, and the progression status should be confirmed at a later time by the review panel (or Principal Investigator).

#### 11.1.3.3 Evaluation of New Lesions

The finding of a new lesion should be unequivocal (i.e. not due to difference in scanning technique, imaging modality, or findings thought to represent something other than tumor (for example, some ‘new’ bone lesions may be simply healing or flare of pre-existing lesions). However, a lesion identified on a follow-up scan in an anatomical location that was not scanned at baseline is considered new and will indicate PD. If a new lesion is equivocal (because of small size etc.), follow-up evaluation will clarify if it truly represents new disease and if PD is confirmed, progression should be declared using the date of the initial scan on which the lesion

was discovered.

#### 11.1.3.4 Evaluation of Best Overall Response

The best overall response is the best response recorded from the start of the treatment until disease progression/recurrence (taking as reference for progressive disease the smallest measurements recorded since the treatment started). The patient's best response assignment will depend on the achievement of both measurement and confirmation criteria.

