#### Prohibited Concomitant Medications

Subjects are prohibited from receiving the following therapies during the Screening and Treatment Phase of this trial:

- Antineoplastic systemic chemotherapy or biological therapy
- Immunotherapy not specified in this protocol
- Chemotherapy not specified in this protocol
- Biologic or targeted agents not specified in this protocol
- Investigational agents other than pembrolizumab
- Radiation therapy
- Any systemically active oral, injected, or implanted hormonal method of contraception except for progesterone coated intrauterine devices (IUDs) that had been previously implanted.
- Estrogen replacement therapy.
- Live vaccines within 28 days prior to the first dose of trial treatment and while participating in the trial. Examples of live vaccines include, but are not limited to, the following: measles, mumps, rubella, varicella/zoster, yellow fever, rabies, BCG, and typhoid vaccine.
- Systemic glucocorticoids for any purpose other than to modulate symptoms from an event of clinical interest of suspected immunologic etiology. The use of physiologic doses of corticosteroids (10 mg prednisone by mouth daily or equivalent) is allowed..
- Care should be taken with concomitant use of strong CYP3A4 inhibitors/inducers (e.g., ketoconazole and itraconazole; see Appendix B) and eribulin mesylate. An alternate medication with no or minimal potential to inhibit CYP3A4 should be considered. If a strong CYP3A4 inhibitor is co-administered with eribulin mesylate, patients should be closely monitored for adverse reactions.

Subjects who, in the assessment by the investigator, require the use of any of the aforementioned treatments for clinical management should be removed from the trial. Subjects may receive other medications that the investigator deems to be medically necessary.

There are no prohibited therapies during the Post-Treatment Follow-up Phase.

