- g. For any subject who showed first radiologic evidence of progressive disease (PD) by RECIST 1.1 (see Section 11.1.4) and is deemed clinically stable (see section 5.6), it is at the discretion of the investigator to continue treating the subject until progression is confirmed at least 4 weeks from the date of the first radiologic evidence of PD. If progression is confirmed, the subject will be discontinued from study treatment. Otherwise, the subject will continue treatment and radiographic scans. Any subject who had initial radiologic progression and is deemed clinically unstable should be discontinued from both study drugs and no subsequent scan for confirmation is required.
- h. Tumor assessments should continue as scheduled for participants on Arm B who crossover to receive pembrolizumab.
- i. During follow-up of patients who went off study for reasons other than PD, tumor assessments should continue every 9 to 12 weeks from the date of the last assessment until progressive disease is documented
- j. Optional biopsy should be obtained within 7 days before starting protocol therapy. See Section 9, appendices, and lab manual for biopsy handling and processing instructions.
- k. Optional tumor biopsy should be offered only in patients who go off study for progressive disease. See Section 9, appendices, and lab manual for biopsy handling and processing instructions. For patients randomized for the eribulin mesylate arm who wish to cross over to pembrolizumab arm, a biopsy at progression is mandatory for those whose disease is amenable for biopsy.
- l. 1 block or 20 unstained slides should be collected. If archival tissue is not available, patients with safely accessible disease should have a baseline biopsy.
- m. Off treatment visit is to occur within 30 days of final administration of study treatment. End of treatment assessments do not have to be repeated if the same assessments were performed within 7 days prior to the visit.
- n. Research blood should only be collected on patients who come off treatment for progressive disease.
- o. Optional blood collection for immune cells/cfDNA may be offered to patients who develop progressive disease during follow-up.
- p. Survival status should be collected annually, either by review of the medical record or by phone call (see Section 5.8).

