#### 11.1.4 Duration of Response

Duration of overall response: The duration of overall response is measured from the time measurement criteria are met for CR or PR (whichever is first recorded) until the first date that recurrent or progressive disease is objectively documented (taking as reference for progressive disease the smallest measurements recorded since the treatment started, or death due to any cause. Participants without events reported are censored at the last disease evaluation).

Duration of overall complete response: The duration of overall CR is measured from the time measurement criteria are first met for CR until the first date that progressive disease is objectively documented, or death due to any cause. Participants without events reported are censored at the last disease evaluation.

Duration of stable disease: Stable disease is measured from the start of the treatment until the criteria for progression are met, taking as reference the smallest measurements recorded since the treatment started, including the baseline measurements.

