#### 11.3.1.5 Immune-Related Best Overall Response Using irRECIST (irRECIST BOR)

irRECIST BOR is the best confirmed overall response over the study as a whole, recorded between the date of first dose until the last tumor assessment before subsequent therapy (except for local palliative radiotherapy for painful bone lesions) for the individual subject in the study. For the assessment of irBOR, all available assessments per subject are considered.

irRECIST CR or irRECIST PR determinations included in the irRECIST BOR assessment must be confirmed by a second (confirmatory) evaluation meeting the criteria for response and performed no less than 4 weeks after the criteria for response are first met.

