### **13.5 Analysis of Secondary Endpoints**

#### Efficacy Endpoints

All patients who initiated protocol therapy will be evaluated for PFS per irRECIST criteria, ORR, CBR, and OS. ORR and CBR will be evaluated using RECIST 1.1 and irRECIST criteria (as defined in Section 11.3). DOR will be evaluated among patients who had CR or PR. All these endpoints will be estimated separately in the two treatment arms.

The objective response rate (CR + PR) and immune-related response rate (irCR + irPR) will be reported by arm with 90% exact confidence intervals. Objective response rate and immune-related response rate will be compared between Arm A and Arm B, respectively using a Pearson

chi-squared test for difference in proportions with a one-sided  $\alpha$  of 0.1.

Clinical benefit is defined as CR, PR or SD  $\geq$  27 weeks. Clinical benefit will be calculated using RECIST 1.1 and irRECIST criteria, respectively. Clinical benefit rate (CR+PR+SD $\geq$ 27 wks) per RECIST 1.1 and irRECIST criteria will be reported respectively with 95% exact confidence intervals. CBR will be compared between two treatment arms using a Pearson chi-squared test for difference in proportions with a one-sided  $\alpha$  of 0.1.

PFS per irRECIST and OS will be also analyzed using Kaplan-Meier product-limit estimates and 95% confidence bands. PFS per irRECIST is defined as the time from study randomization to disease progression per irRECIST or death due to any cause, whichever occurred first. Patients alive without disease progression per irRECIST are censored at the date of last disease evaluation. OS is defined as the time from study randomization to death due to any cause. Patients will be censored at the date they were last known alive. The hazard ratio for each time-to-event endpoint will be estimated with 95% confidence intervals derived from the Cox proportional hazard model, but no hypothesis testing will be conducted.

DOOR is defined as the time from CR or PR achieved until renewed disease progression is detected. DOOR will be calculated per RECIST 1.1 and irRECIST criteria, respectively, and descriptive statistics will be used to summarize the intervals observed by arm.

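### RECIST response, duration of response and stable-disease duration have no cut at new anticancer therapy, so a result reached on a later-line drug can be credited to the randomized arm

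*Combined protocol and SAP*

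**What the plan says.** **RECIST definitions.**
- Best overall response, 11.1.3.4: "The best overall response is the best response recorded from the start of the treatment until disease progression/recurrence".
- Duration of response, 11.1.4: it runs "until the first date that recurrent or progressive disease is objectively documented", or to death. Otherwise, "Participants without events reported are censored at the last disease evaluation".
- Duration of response, 13.5: it "is defined as the time from CR or PR achieved until renewed disease progression is detected". Death is not mentioned there.
- Stable disease, 11.1.4: "Stable disease is measured from the start of the treatment until the criteria for progression are met". This feeds CBR, which 11.1.5 and 13.5 define as CR, PR or SD of at least 27 weeks.

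**irRECIST.** Section 11.3.1.5 counts best overall response only "until the last tumor assessment before subsequent therapy", with an exception for local palliative radiotherapy to painful bone lesions.

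**After treatment stops.** Section 5.6.1 states: "There are no prohibited therapies during the Post-Treatment Follow-up Phase". For patients who leave for reasons other than progression, footnote i of the Study Calendar says that "tumor assessments should continue every 9 to 12 weeks from the date of the last assessment until progressive disease is documented". Section 5.8 asks for the same scans where possible.

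**Use of the endpoints.** Section 13.5 reports ORR and CBR under both criteria sets and compares each between arms with a Pearson chi-squared test at one-sided 0.1. Duration of response is only described.

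**The concern.** Take an Arm B patient who stops eribulin for toxicity at week 12 with stable disease, starts another chemotherapy at week 14, and shows a partial response, or is still stable, at week 27. No RECIST progression has occurred, so the window in 11.1.3.4 is still open and the SD clock in 11.1.4 is still running. Read literally, the patient is a RECIST responder, or has clinical benefit, on the randomized treatment. Under 11.3.1.5 the same patient's irRECIST best response is fixed before the new drug.

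Two things are at stake. First, RECIST ORR and CBR can include an effect of non-protocol drugs. The amount depends on how often each arm stops all protocol therapy without progression, and this need not be equal between one drug and two. Second, a difference between RECIST and irRECIST results may partly reflect the length of the window and not the criteria.

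**Working it through.** **1. Is there a cut anywhere?**

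| Quantity | Where | Ends at | Cut at new therapy |
|---|---|---|---|
| RECIST best response | 11.1.3.4 | progression or recurrence | no |
| Duration of response | 11.1.4 | progression or death | no |
| Duration of response, both criteria sets | 13.5 | progression | no |
| SD duration | 11.1.4 | progression | no |
| irRECIST best response | 11.3.1.5 | last assessment before subsequent therapy | yes |

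No general rule elsewhere in the protocol supplies the missing cut.

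**2. Can a patient start another drug while the RECIST window is open?** Yes. Section 5.7 lists several reasons for stopping other than progression. Section 5.6.1 has patients who need a prohibited treatment removed from the trial. Section 11.1.3.4 covers symptomatic deterioration without objective progression and asks that progression still be documented after treatment ends. Section 5.7 also limits the Second Course Phase to patients who have had no systemic cancer treatment other than eribulin since their last pembrolizumab dose, so such treatment is foreseen. Arm B crossover is not a route: section 5.1 places it at progression, when the RECIST window has closed.

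**3. Size, Arm B, for illustration only.** The plan gives no figure on this point to reproduce. Its stated power of 83% concerns PFS and is not affected.

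Inputs from the documents:
- median PFS of 4.1 months (13.2);
- 44 patients per arm (13.2);
- 13% stopping eribulin for adverse events in the pivotal phase III trial (2.4);
- eribulin ORR of 11.0% in the phase III comparison with capecitabine (2.4).

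Assumptions:
- PFS is exponential, and the progression hazard is unchanged by stopping or switching;
- 13% to 25% stop all protocol therapy before 27 weeks (6.2 months), uniformly in time;
- 50% to 100% of those still progression-free then switch;
- all responders (11%) respond before stopping and are progression-free at 27 weeks;
- the later-line response rate is 11.5%, close to the 11-12% eribulin figures in 2.4.

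Progression-free at 27 weeks: exp(-ln 2 x 6.2/4.1) = exp(-1.048) = 35.06%.

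Responders already count as clinical benefit with or without a cut, so they are removed: 35.06% - 11% = 24.06%.

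Added to CBR = 24.06% x share stopping x share switching:
- low: 24.06% x 0.13 x 0.5 = 1.6 points (0.7 of 44 patients);
- high: 24.06% x 0.25 x 1.0 = 6.0 points (2.6 of 44 patients).

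Share still progression-free at a uniform stopping time: (1 - 0.3506)/1.048 = 0.620.

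Added to ORR = 0.620 x share stopping x share switching x 0.115:
- low: 0.620 x 0.13 x 0.5 x 0.115 = 0.5 points (0.2 of 44 patients);
- high: 0.620 x 0.25 x 1.0 x 0.115 = 1.8 points (0.8 of 44 patients).

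The ORR line treats every switcher as a non-responder at the switch, so it is slightly high.

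**4. Arm A.** The same calculation cannot be carried over. Sections 5.4, 5.5 and 6 let a patient who stops one drug for toxicity continue the other on protocol. A single-agent discontinuation rate is therefore not a rate of leaving all protocol therapy.

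**The case against.** The strongest objection is that following patients to progression whatever they take next is a legitimate treatment-policy choice. Section 13.4 says that inference follows intent-to-treat, and RECIST PFS is defined the same way. With a cut, a patient could be progression-free at 27 weeks for PFS and yet fail on CBR. This argument stands for PFS, which should stay as it is. It is weaker for response endpoints: the intent-to-treat statement sits under the primary PFS analysis, and the plan itself stops irRECIST best response at subsequent therapy.

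Three stronger readings are tempting, and the documents do not support them.
- *That later-line results are in fact being credited.* No switching rate is given, and section 5.8 asks for off-treatment scans only where possible. The text shows that it can happen, not how often.
- *That CBR moves by the full progression-free share.* Multiplying 35.06% by the stopping and switching shares gives 2.3 to 8.8 points, but that share includes CR and PR patients who have clinical benefit either way. It also places all stopping before week 27, although the 13% in section 2.4 is an overall rate.
- *That the between-arm tests are biased in a known direction.* Both arms can gain, and their rates of complete exit are unknown.

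It is also fair that ORR hardly moves, that duration of response is not tested, and that 11.3.1.5 covers only irRECIST best response. Section 13.5 gives no cut for irRECIST duration of response, so a RECIST-only repair would create a new mismatch.

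**Conclusion.** The gap is real. Read as written, the RECIST rules can credit a later-line response or stability to the randomized arm, and they differ from the irRECIST rule for the same patient. CBR is the endpoint that matters: about 1.6-6.0 points in Arm B under the stated assumptions. ORR moves by about 0.5-2 points, at most about 1 of 44 patients. These figures rest on assumed stopping, switching and response rates and show scale only. No Arm A figure, net bias or error rate should be quoted. The endpoints are secondary, and the sample size, event count and power are unaffected. The change is worth making before analysis because ORR and CBR are formally compared and the plan already contains the rule for one criteria set.

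**What to change.** Amend 11.1.3.4, 11.1.4 and 13.5 as follows.
- Base RECIST best overall response and SD of at least 27 weeks on assessments up to the earlier of RECIST progression or the last tumor assessment before any non-protocol anticancer therapy. Keep the palliative-radiotherapy exception of 11.3.1.5. SD that reaches 27 weeks only after that point does not count as clinical benefit.
- Censor duration of response at that same last assessment, under both RECIST and irRECIST.
- Leave the primary PFS definition unchanged.

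The cost is a few sentences plus recording the start date of new anticancer therapy, an event that section 7.6 already uses as a boundary for safety reporting. Reported ORR and CBR may be slightly lower.

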#### For Participants with Measurable Disease (*i.e.*, Target Disease)

Target Lesions	Non-Target Lesions	New Lesions	Overall Response	Best Overall Response when Confirmation is Required*
CR	CR	No	CR	4 wks Confirmation**
CR	Non-CR/Non-PD	No	PR	4 wks Confirmation**
CR	Not evaluated	No	PR	
PR	Non-CR/Non-PD/not evaluated	No	PR	
SD	Non-CR/Non-PD/not evaluated	No	SD	
PD	Any	Yes or No	PD	no prior SD, PR or CR
Any	PD***	Yes or No	PD	
Any	Any	Yes	PD	

\* See RECIST 1.1 manuscript for further details on what is evidence of a new lesion.  
 \*\* Only for non-randomized trials with response as primary endpoint.  
 \*\*\* In exceptional circumstances, unequivocal progression in non-target lesions may be accepted as disease progression.

Note: Participants with a global deterioration of health status requiring discontinuation of treatment without objective evidence of disease progression at that time should be reported as “*symptomatic deterioration*.” Every effort should be made to document the objective progression even after discontinuation of treatment.

#### For Participants with Non-Measurable Disease (*i.e.*, Non-Target Disease)

Non-Target Lesions	New Lesions	Overall Response
CR	No	CR
Non-CR/non-PD	No	Non-CR/non-PD*
Not all evaluated	No	not evaluated
Unequivocal PD	Yes or No	PD
Any	Yes	PD

\* ‘Non-CR/non-PD’ is preferred over ‘stable disease’ for non-target disease since SD is

increasingly used as an endpoint for assessment of efficacy in some trials so to assign this category when no lesions can be measured is not advised

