### **3.1 Eligibility Criteria**

3.1.1 Patients must have histologically or cytologically confirmed Stage IV invasive breast cancer. Patients without pathologic or cytologic confirmation of metastatic disease should have unequivocal evidence of metastasis from physical examination or radiologic evaluation.

- 3.1.2 Subjects must have at least one lesion that is not within a previously radiated field that is evaluable on computerized tomography (CT) or magnetic resonance imaging (MRI) scan per RECIST version 1.1. If the subject's only evaluable disease is within a previously radiated field, it must have demonstrated progression since the time of radiation.
- 3.1.3 Participants must have HR positive, HER2-negative breast cancer (ER>1% and/or, PR>1%, HER2-negative per ASCO CAP guidelines, 2013 resulted on the primary tumor and/or a metastatic lesion).
- 3.1.4 Participants must have already received or been intolerant to at least two lines of hormonal therapies (including the adjuvant or metastatic setting) or be appropriate candidates for chemotherapy
- 3.1.5 **Prior chemotherapy:**  
Participants are allowed to have received up to 2 prior lines of chemotherapy in the metastatic setting. If a prior chemotherapy was given for less than 1 cycle, it will not be counted as a prior line. The last dose of chemotherapy must be  $\geq$ 14 days prior to initiation of study therapy. Participants should be adequately recovered from acute toxicities of prior treatment. No prior treatment with eribulin mesylate is allowed.
- 3.1.6 **Prior biologic therapy:** The last dose of biologic or investigational therapy must be  $\geq$ 21 days prior to initiation of study therapy.
- 3.1.7 **Prior hormonal therapy:** Hormonal therapy must have been discontinued  $\geq$ 14 days prior to initiation of study therapy. However, continuation of ovarian suppression is allowed.
- 3.1.8 **Prior radiation therapy:** Participants may have received prior radiation therapy in either the metastatic or early-stage setting. Radiation therapy must be completed  $\geq$ 14 days prior to initiation of study therapy.
- 3.1.9 **Prior targeted therapy:** Targeted therapy must have been discontinued  $\geq$  14 days prior to initiation of study therapy.
- 3.1.10 **Biphosphonates/Denosumab:** Participants on bisphosphonates/denosumab may continue receiving bisphosphonate therapy during study treatment.

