### 11.1.1 Definitions

**Evaluable for Target Disease response.** Only those participants who have measurable disease present at baseline, have received at least one cycle of therapy, and have had their disease re-evaluated will be considered evaluable for target disease response. These participants will have their response classified according to the definitions stated below. (Note: Participants who exhibit objective disease progression prior to the end of cycle 1 will also be considered evaluable.)

**Evaluable Non-Target Disease Response.** Participants who have lesions present at baseline that are evaluable but do not meet the definitions of measurable disease, have received at least one cycle of therapy, and have had their disease re-evaluated will be considered evaluable for non-target disease. The response assessment is based on the presence, absence, or unequivocal progression of the lesions.

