### 11.1.2 Disease Parameters

**Measurable disease.** Measurable lesions are defined as those that can be accurately measured in at least one dimension (longest diameter to be recorded) as  $\geq 20$  mm by

chest x-ray or  $\geq 10$  mm with CT scan, MRI, or calipers by clinical exam. All tumor measurements must be recorded in millimeters (or decimal fractions of centimeters).

Note: Tumor lesions that are situated in a previously irradiated area are not considered measurable.

Malignant lymph nodes. To be considered pathologically enlarged and measurable, a lymph node must be  $\geq 15$  mm in short axis when assessed by CT scan (CT scan slice thickness recommended to be no greater than 5 mm). At baseline and in follow-up, only the short axis will be measured and followed.

Non-measurable disease. All other lesions (or sites of disease), including small lesions (longest diameter  $< 10$  mm or pathological lymph nodes with  $\geq 10$  to  $< 15$  mm short axis), are considered non-measurable disease. Bone lesions, leptomeningeal disease, ascites, pleural/pericardial effusions, lymphangitis cutis/pulmonitis, inflammatory breast disease, abdominal masses (not followed by CT or MRI), and cystic lesions are all considered non-measurable.

Note: Cystic lesions that meet the criteria for radiographically defined simple cysts should not be considered as malignant lesions (neither measurable nor non-measurable) since they are, by definition, simple cysts.

'Cystic lesions' thought to represent cystic metastases can be considered as measurable lesions, if they meet the definition of measurability described above. However, if non-cystic lesions are present in the same participant, these are preferred for selection as target lesions.

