#### 11.1.5 Clinical Benefit rate

Clinical benefit rate: defined as CR, PR and stable disease (SD)  $\geq$  27 weeks.

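### Read literally, the clinical benefit rate under RECIST 1.1 gives no credit to long-stable patients without measurable disease, because Non-CR/non-PD is not in its definition

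*Combined protocol and SAP*

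**What the plan says.** **Who can enrol.** Criterion 3.1.2 asks for evaluable disease and does not require measurable disease: "Subjects must have at least one lesion that is not within a previously radiated field that is evaluable". Section 11.1.1 provides a response assessment for "Participants who have lesions present at baseline that are evaluable but do not meet the definitions of measurable disease". Section 11.1.2 lists what is non-measurable, beginning with "Bone lesions, leptomeningeal disease, ascites, pleural/pericardial effusions".

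**What labels they can receive.** Section 11.1.3.4 has a separate RECIST 1.1 table for participants with non-measurable disease. Its outcomes are CR, Non-CR/non-PD, not evaluated and PD. It has no PR or SD row. The footnote prefers Non-CR/non-PD to stable disease, on the ground that SD is increasingly used as an efficacy endpoint, and ends "so to assign this category when no lesions can be measured is not advised".

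**What counts as benefit.** Section 13.5 reads "Clinical benefit is defined as CR, PR or SD", with a 27-week minimum for SD. Section 11.1.5 names the same three categories. Neither mentions Non-CR/non-PD.

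**Who is in the denominator.** Section 13.5: "All patients who initiated protocol therapy will be evaluated for PFS per irRECIST criteria, ORR, CBR, and OS". CBR is calculated under RECIST 1.1 and irRECIST and compared between arms by a Pearson chi-squared test at one-sided 0.1.

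**The concern.** Each rule is reasonable alone, but together they leave one group without a route to clinical benefit by disease control. A patient with measurable disease who is stable for 27 weeks is a benefit. A patient with only bone lesions and the same course carries a label that the definition does not count, and stays in the denominator. The same patient contributes a long progression-free time to the primary analysis, so the two endpoints would describe one outcome in opposite ways.

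At stake is a formally compared secondary endpoint. Literal scoring lowers CBR in both arms. It removes more patients in absolute terms from the arm with better disease control, so the tested difference shrinks. If the rule stays open, a choice that moves the result would be made in an open-label trial, by individual assessors or after data have been seen.

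**Working it through.** **The plan's own figure.** Section 13.2 states 83% power for PFS: 70 events, HR 0.58, one-sided alpha 0.1. The Schoenfeld form gives Φ(√70/2 × |ln 0.58| − 1.2816) = Φ(2.279 − 1.282) = 0.841. Adding the futility look at Z = 0 and half the information gives 0.826, or 0.830 with HR = 4.1/7.1. The 83% reproduces and does not depend on this point. The documents state no power for CBR, so what follows is an illustration and does not re-derive a planned figure.

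**Inputs from Section 13.2:** median PFS 4.1 months (Arm B) and 7.1 months (Arm A), constant hazard, 44 patients per arm. **From Section 13.5:** one-sided alpha 0.1 and the 27-week threshold.

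**Assumptions not in the documents**
- Clinical benefit equals being progression-free at 27 weeks.
- PFS is the same in patients with and without measurable disease.
- The non-measurable share f is equal in both arms; 10%, 20% and 30% are assumed values.
- No patient without measurable disease reaches CR.

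**Step 1: true benefit.** 27 weeks = 27 × 7 / 30.4375 = 6.21 months.
- Arm B: exp(−ln 2 × 6.21 / 4.1) = 0.350
- Arm A: exp(−ln 2 × 6.21 / 7.1) = 0.545

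**Step 2: benefit as scored.** Literal scoring multiplies each rate by (1 − f). Benefit patients lost are 44 × 0.545 × f in Arm A and 44 × 0.350 × f in Arm B.

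**Step 3: power.** All pairs of binomial counts with 44 per arm are enumerated, and the pair rejects if the pooled z-statistic is at least 1.2816.

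| Assumed f | CBR, Arm B | CBR, Arm A | Difference (points) | Benefits lost, A / B | Power |
|---|---|---|---|---|---|
| 0% | 35.0% | 54.5% | 19.5 | 0 / 0 | 73% |
| 10% | 31.5% | 49.1% | 17.6 | 2.4 / 1.5 | 68% |
| 20% | 28.0% | 43.6% | 15.6 | 4.8 / 3.1 | 62% |
| 30% | 24.5% | 38.2% | 13.7 | 7.2 / 4.6 | 55% |

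A normal approximation gives 72%, 66%, 60% and 54%. The ratio of the two rates stays at 0.545 / 0.350 = 1.56 throughout; only the absolute difference shrinks.

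**Step 4: the alternative of restricting the denominator.** Dropping patients without measurable disease leaves about 40, 35 or 31 per arm at true rates of 35.0% and 54.5%. Power is then about 70%, 63% or 60%. This restores the rates but loses patients.

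**irRECIST, passages side by side.** The overall-response definition in 11.3.1.4 makes stable disease the residual category with no measurability condition, so a stable patient without measurable disease could count. Section 11.3.1.3 says the PR and SD terms do not apply to non-target lesions, and the summary table has no row for a patient without target lesions. The result is undetermined.

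**The case against.** The strongest reply is that no sentence scores Non-CR/non-PD as non-benefit. The footnote is advisory and concerns a label, and an assessor could still record SD. That stands as far as it goes: the loss of credit follows from reading the rules together and is not an express instruction. It does not remove the problem, because following the plan's stated preference gives non-benefit and departing from it gives benefit.

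The footnote also has a reason: where nothing can be measured, stability is a weaker observation. Counting it as benefit should therefore be a deliberate choice, backed by an analysis without it.

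A reader might infer more than the documents support:
- *That patients without measurable disease can never show benefit.* The table allows them CR, which counts, as well as PD and not evaluated. The gap concerns only those who are stable.
- *That irRECIST CBR has the same defect.* Sections 11.3.1.3 and 11.3.1.4 pull in different directions, so there the rule is ambiguous.
- *That literal scoring would manufacture a treatment effect.* With no true effect, a 35% benefit rate and shares of 10% in Arm A and 30% in Arm B, the scored difference would be 0.35 × (0.30 − 0.10) = 7 points. That imbalance is unusual, however. Around a common share of 20% the standard error is √(2 × 0.2 × 0.8 / 44) = 0.085, so a 20-point gap is about 2.3 standard errors. With equal expected shares under randomisation, the expected effect is attenuation.

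**Conclusion.** The concern holds for RECIST 1.1 CBR, in limited form. A patient without measurable disease who is progression-free for 27 weeks or more without CR has, on a literal reading, no category that counts as clinical benefit, but remains in the tested denominator. CBR is lowered in both arms and the absolute difference narrows.

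The size depends on the non-measurable share, which the documents do not give. Under the four assumptions above, a share of 10% to 30% takes the difference from 19.5 to between 17.6 and 13.7 points, and power from 73% to between 68% and 55%. The 73% is itself an illustration.

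Primary PFS, its 70 events and its 83% power are unaffected. This is a correction to a secondary endpoint that should be made before analysis; it does not threaten the trial's main conclusion.

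**What to change.** - In 11.1.5 and 13.5, count Non-CR/non-PD lasting at least 27 weeks as clinical benefit for patients without measurable disease at baseline, alongside CR, PR and SD of at least 27 weeks.
- Apply the same rule to irRECIST CBR, and reconcile 11.3.1.3 with 11.3.1.4 for patients without target lesions.
- Report CBR in patients with measurable disease at baseline as a sensitivity analysis, and give the number without measurable disease in each arm.

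The cost is wording and one extra table, with no new data collection. The downside is small: Non-CR/non-PD is less precise than measured SD, and the sensitivity analysis shows how far the result depends on it. If the team instead prefers to exclude these patients from CBR, the denominator should say so in advance; under the same assumptions that choice gives power of about 70%, 63% or 60%.
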